A total of fifteen New Zealand rabbits were enrolled randomly into the following groups: six animals received PerClot; six animals received Arista; and three animals underwent sham operated procedure. On the day of implantation, rabbits were anesthetized and an incision was made over the abdomen to access the intraperitoneal space. Animals enrolled in either PerClot or Arista groups received a pre-weighed amount (10 grams) of the appropriate hemostat delivered directly into the peritoneal cavity. Animals enrolled in the sham operated group were immediately closed following access to the peritoneal cavity. Blood glucose levels were measured at baseline (fasted levels), and at 1 hour, 2 hours, 4 hours, 6 hours, 9 hours, 12 hours, 24 hours, 48 hours, 72 hours, and 96 hours after delivery of either PerClot, Arista, or sham operation. Following the measurement of blood glucose at 96 hours post-operation, all animals were euthanized and the peritoneal cavity was examined grossly for any remaining hemostat as well as using the iodine test for presence of any residual starch based material.

Baseline blood glucose levels were similar for all three groups (153.61 mg/dL, 148.17 mg/dL, and 141.89 mg/dL for PerClot, Arista, and Sham groups, respectively) and all three treatment groups had mean baseline blood glucose levels within normal range for New Zealand White rabbits (100 – 190 mg/dl). Blood glucose levels 1 hour post-operatively were significantly higher than baseline blood glucose for all three groups ($p<0.05$), with glucose levels remaining relatively high at 2 hours post-operatively for animals treated with PerClot or Arista. Glucose levels of PerClot and Arista animals at 2 hours were almost equivalent while slightly higher than glucose levels in Sham operated control animals. By 4 hours, glucose levels for all three groups were similar and remained normal for the remainder of the study.

It was concluded that known structural differences in the polysaccharide molecules and the rates of breakdown of the two products did not result in elevated systemic blood glucose levels during the degradation of PerClot and Arista in a rabbit model. As all groups experienced brief elevation of blood glucose levels at 1 and 2 hours post-surgery, post-operative stress and excitement most likely attributed to those slight elevations.

Furthermore, no residual starch based material was found in the peritoneal cavity in any of the study rabbits at 96 hours post application.

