6.4.4 Postoperative Evaluations

All subjects will undergo the following assessments within 24 hours postoperatively:

- Clinical signs or symptoms of bleeding;
- Any blood product administration;
- Reoperation;
- Use of any blood modifiers insulin, or blood sugar lowering medications or reversal drugs;
- Drainage volume within the first 24 hours postoperatively and time of drain volume measurement, as applicable;

- Complete blood count, coagulation status (platelet count, PTT, INR, and fibrinogen) and Complement C3;
- Incidence of any complications/AEs;
- Clinical signs or symptoms of embolism or thrombosis; and
- Thromboembolism Assessment.

All subjects will undergo a blood glucose assessment at the following time points:

- After randomization (prior to application of study device);
- Within 1 hour following study device application;
- 6 hours (\pm 30 min) following study device application;
- 12 hours (\pm 30 min) following study device application; and
- 24 hours (\pm 30 min) following study device application.

Note: Blood glucose measurements should be evaluated with venous blood draw or the Nova StatStrip blood glucose meter. Blood glucose measurements should not be evaluated with any other blood glucose meter.

The Postoperative eCRF and Laboratory eCRF must be completed for the postoperative evaluation. The Blood Modifiers/Insulin or Blood Sugar Lowering Medications eCRF, Adverse Event eCRF, and Reoperation eCRF should also be completed as applicable.

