An adverse event is any untoward medical occurrence in a clinical study subject. An adverse event would be any unfavorable or unintended sign, symptom, or disease that appears or worsens during the clinical study regardless of the relationship to the device. An adverse event would include any clinically significant laboratory value, as determined by the investigator, for routine laboratory results. An abnormal laboratory value is considered clinically significant if the investigator determines that the subject requires treatment, or if he/she would conduct a repeat test to verify normalization.

Adverse Event Reports

Investigator reports of all serious adverse events, injuries, and deaths given to the Sponsor, the IRB, and the FDA or appropriate regulatory body.

Allergic Reaction

The body's response to an allergic stimulus. This can be localized to one area or generalized and may include rash, itching, hives, swelling, difficulty breathing, and/or low blood pressure.

Anatomic Application Site

Approximate surface area of the target application site, measured by adding one (1) centimeter to both greatest perpendicular distances of the bleeding site and multiplying the two values.

$$\begin{aligned} \text{Anatomic Application Site (cm}^2\text{)} \\ = & (\text{greatest perpendicular length, cm} + 1 \text{ cm}) \\ \cdot & (\text{greatest perpendicular width, cm} + 1 \text{ cm}) \end{aligned}$$

Anatomic Site

Approximate surface area of bleeding site, measured by multiplying the greatest perpendicular distances of the bleeding site.

$$\begin{aligned} \text{Anatomic Site (cm}^2\text{)} = & (\text{greatest perpendicular length, cm}) \\ \cdot & (\text{greatest perpendicular width, cm}) \end{aligned}$$

Bleeding Site

True surface area of wound, or lesion from which blood egress is observed..

Blood Modifiers

Drug category that includes agents that modify properties of human blood (anticoagulants, antiplatelet agents, hemostatics, heparin antagonists, thrombolytic agents).

Case Report Form (CRF)

A form designated to record all of the protocol-required information that is to be reported to the Sponsor on a clinical investigation subject.

Clinical Investigation

A systematic study designed to evaluate a product (drug, device, or biologic) using human subjects in the treatment, prevention, or diagnosis of a disease or condition as determined by the product's benefits relative to its risks.

Clinical Research

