- In subjects who have undergone platelet receptor GP IIb/IIIa antagonist therapy less than 48 hours prior to surgery;

- In subjects who have been treated with an investigational product and have not completed the entire follow-up period for that investigational product;
- In subjects who are pregnant (as confirmed by a pregnancy test), planning on becoming pregnant during the follow-up period, or actively breast-feeding;
- In subjects with poor blood glucose control as per glycosylated hemoglobin > 9% and
- In subjects with an active or potential infection at the surgical site, or whose surgical wound is defined as wound classification CO (Contaminated) or D (Dirty or Infected) based upon the Centers for Disease Control and wound classification system.

NOTE: PerClot is predicted to activate Complement C3 because of its activity and fluid absorption capacity.

NOTE: The expected rate of absorption will vary depending on anatomic location. Elevated peri-operative blood glucose levels may also be associated with increased rate of wound infection. Elevated blood glucose levels in the immediate postoperative period may affect wound healing.

NOTE: The safety and effectiveness of PerClot have not been clinically evaluated in pediatric patients, on ophthalmic or neurologic tissues, or in laparoscopic cases.

NOTE: Once hemostasis is achieved, excess PerClot should be removed from the site of application by irrigation and aspiration. In an in vitro study where PerClot was agitated to ensure complete hydration, the average maximum swell capacity for each gram of PerClot in deionized water, saline, and blood were 59.7 mL, 27.1 mL, and 11.0 mL, respectively. Under these conditions the time to maximum swelling was 10 minutes. Dry, white PerClot should be removed. The possibility of the product interfering with normal function and/or causing compression necrosis of surrounding tissues due to swelling is reduced by removal of excess dry material.

Precautions

- PerClot is not recommended as a primary treatment for coagulation disorders.
- PerClot is intended to be used in a dry state. Contact with fluids prior to application will result in the loss of hemostatic properties.

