14. Albumin	 g/dL	 1	 1 Yes	 0 No	 1 Yes*  0 No
15. HbA1c	 %	 1	 1 Yes	 0 No	 1 Yes*  0 No
16. C3	 mg/dL	 1	 1 Yes	 0 No	 1 Yes*  0 No
17. Blood Glucose [†]	 mg/dL	 1	 1 Yes	 0 No	 1 Yes*  0 No

Note: Blood glucose measurement should be evaluated by a venous blood draw or Nova StatStrip blood glucose meter.

Preoperative Lab work will occur no more than 1 month (30 days) prior to surgery.

Please complete the Adverse Event Form after device application only.*[†]Blood glucose levels should be collected within 1hr (\pm 30 minutes) after device application, 6 hours (\pm 30 minutes), 12 hours (\pm 30 minutes), 24 hours (\pm 30 minutes).**

Reoperation DRAFT Form
Form 10Form completed by: _____
Date form completed: ___ / ___ / ___Subject Initials: Subject Number: Surgery Date (DD/MMM/YYYY): / / Visit Type: 9 Reoperation

PROCEDURE INFORMATION

1. Reason for reoperation:
2. Procedure(s) performed: a.
b.
c.
3. Was this reoperation for hemostatic agent application site bleeding?
 1 Yes
 0 No
 - a. If yes, methods used to attempt to obtain hemostasis (check all that apply):
 1 Not applicable
 2 Make-up stitches (# of stitches:)
 3 Other, please specify:
4. Was the hemostatic device visually apparent?
 1 Yes, please comment:
 0 No

Please complete the Adverse Event Form for all Reoperations.

Principal Investigator Signature

 / /

Date (DD/MMM/YYYY)

Adverse Event DRAFT Form
Form 11A

Form completed by: _____
Date form completed: ___ / ___ / ___

Subject Initials: Subject Number:

ADVERSE EVENT

1. Description of adverse event:

2. CTCAE-2009* short name for adverse event: 3. Date of onset (DD/MMM/YYYY): / /

4. Severity of adverse event (per CTCAE-2009* grade):

- 1 Grade 1 - Mild; asymptomatic or mild symptoms; clinical or diagnostic observations only; intervention not indicated

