4.4.4 Safety Analyses

Safety data will be summarized by incidence of each adverse event type along with 95% exact confidence intervals. Adverse event rates will be reported as the proportion of subjects who experience an event and the total number of each event type occurring.

Adverse events will be summarized by relatedness, seriousness, and severity. The comparison of safety between treatment arms will be based on Fisher's exact tests for the proportion of subjects with serious device-related adverse events, unanticipated adverse device effects, and frequent adverse events ($\geq 5\%$ overall incidence) in the two treatment groups.

The other following safety endpoints will also be summarized using descriptive statistics:

- Total operative time;
- Hemostasis at 5 to 7 minutes;
- Hemostasis maintenance;
- Total intraoperative estimated blood loss;
- Alternative means required to achieve hemostasis (where applicable);
- Units of blood transfused intraoperatively and postoperatively (where applicable);
- Incidence of reoperation;
- Total hospitalization time;
- Incidence of procedure complications;
- Incidence of adverse events through final follow-up, including, but not limited to:
 - Adhesions or fibrosis;
 - Anaphylaxis;
 - Blockage of the bladder or ureteral lumen;
 - Blockage of the bypass system;
 - Cancer recurrence and/or progression;
 - Compromised attachment of prosthetic devices to bone or tissue;
 - Death;
 - Embolism;
 - Failure of deep or superficial wound healing;
 - Failure to obtain hemostasis;
 - Fever;
 - Hemorrhage;
 - Infection;
 - Peri-operative hyperglycemia;
 - Exacerbation of surgical procedure-associated adverse events;
 - Swelling and compression of pressure-sensitive tissues and structures;
 - Thromboembolism;
 - Thrombosis; and
 - Toxicity.

Safety analyses are descriptive in nature. There are no formal hypothesis tests associated with these outcomes. All safety analyses will be performed on the ITT population.

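### Glucose and C3 are measured in every subject and both are tied to named device risks, but no by-arm summary of the measured values is planned; hyperglycemia is compared only as an investigator-called event, subject to a 5% incidence threshold or a restricted event class

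*SAP*

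**What the plan says.** **Collection.** Protocol 6.4.4 states "All subjects will undergo a blood glucose assessment at the following time points": after randomization but before the device, a first post-device draw, then 6, 12 and 24 hours. C3 is drawn preoperatively (Protocol 6.4.2) and within 24 hours after surgery (6.4.4).

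**Named risks.** Peri-operative hyperglycemia is a listed possible event of PerClot (Protocol 4.2) and risk item R97 (medium probability, grade 3). C3 activation is risk item R95 (low probability, grade 3). The Instructions for Use add: "PerClot is predicted to activate Complement C3 because of its activity and fluid absorption capacity". Both risk items list the clinical protocol as a preventive action.

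**Analysis.** SAP 4.4.4 summarizes adverse events by type with exact 95% intervals. It applies Fisher's exact test between arms to serious device-related events, unanticipated adverse device effects, and events with at least 5% overall incidence. It then says "The other following safety endpoints will also be summarized using descriptive statistics". Peri-operative hyperglycemia is an adverse-event line in that list. Measured glucose, C3 and C3 activation do not appear, there or in Protocol 6.6.4.

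**Route from laboratory value to event.** The Protocol glossary (Section 13) says: "An abnormal laboratory value is considered clinically significant if the investigator determines that the subject requires treatment", or would repeat the test to confirm that it has returned to normal. Only subjects are blinded (Protocol 6.6.8).

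**First window.** Protocol 6.4.4: "Within 1 hour following study device application". The Laboratory form footnote in Appendix E: "Blood glucose levels should be collected within 1hr", followed by a tolerance of plus or minus 30 minutes.

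**The concern.** The trial gathers objective, scheduled measurements bearing on two risks that its own risk file names. The planned analysis then sees glucose only through a judged event count and does not see C3 by arm at all. Followed as written, the report could show little or no hyperglycemia signal even if glucose ran higher on one device, and it would say nothing about C3 change by arm. At stake is the safety comparison, not the non-inferiority result.

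**Working it through.** **1. Arm size.** The SAP's own figure is power 0.79885 with 154 per arm (Appendix A; 90% vs 90%, margin 0.10, one-sided 0.025, Farrington-Manning score test). With the restricted-variance formula, power = Φ{[0.10 − 1.96·s0]/s1}, I obtain 0.79885. The SAP then allows for 5% loss and plans 162 per arm, 324 in total. The steps below use 162.

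**2. Where each measurement goes.**

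| Measurement | Named analytic use |
|---|---|
| Glucose at randomization | Optional covariate for 7-minute hemostasis (Protocol 6.6.11, SAP 4.6) |
| Glucose within 1 h | Same |
| Glucose at 6, 12, 24 h | None named |
| C3 | Optional covariate for hemostasis; pre- or postoperative value not stated |

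The covariate models estimate association with hemostasis. They do not describe glucose or C3 by arm.

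**3. The incidence threshold.** 0.05 × 324 = 16.2, so 17 subjects are needed. A split of 3 versus 13 is 3/162 = 1.9% against 13/162 = 8.0%, with two-sided Fisher p = 0.018. The total is 16/324 = 4.9%, so the comparison would not be triggered.

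**4. How often the threshold matters.** Let X ~ Bin(162, p1) and Y ~ Bin(162, p2). Exact enumeration gives the table below. The test is taken as two-sided at 0.05, since the SAP gives no level. The event rates are assumptions; the documents give none.

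| True rates | P(X+Y ≥ 17) | P(Fisher p ≤ 0.05), no threshold | P(both) |
|---|---|---|---|
| 2% vs 6% | 0.16 | 0.34 | 0.09 |
| 2% vs 8% | 0.46 | 0.63 | 0.35 |
| 5% vs 10% | 0.96 | 0.32 | 0.31 |
| 5% vs 15% | 1.00 | 0.82 | 0.82 |

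The threshold costs most when events are uncommon overall. At higher rates it hardly matters.

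**5. What the measured values could show.** The 95% half-width for a mean difference is 1.96 × SD × √(2/162) = 1.96 × SD × 0.1111. The difference detectable with 80% power at two-sided 0.05 is (1.96 + 0.84) × 0.1111 × SD, or about 0.31 SD. The SDs are assumed, and all 162 per arm are taken to have values.

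| SD (mg/dL) | Half-width | Detectable difference |
|---|---|---|
| 30 | 6.5 | 9.3 |
| 40 | 8.7 | 12.5 |
| 50 | 10.9 | 15.6 |

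These are not on the same scale as the powers in step 4. They show only that the data already collected would give a usable estimate at each time.

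**6. The window.** Read as 1 hour plus or minus 30 minutes, the form accepts 30 to 90 minutes; Protocol 6.4.4 accepts 0 to 60. A draw at 75 minutes meets the form and breaks the protocol text. A draw at 5 minutes does the reverse.

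**The case against.** The strongest reply is that hyperglycemia is already analyzed. It is a listed adverse event with exact intervals, and it reaches a by-arm Fisher test when frequent or when it falls in a serious device-related or unanticipated class. That stands. A reader might infer that no safety analysis compares hyperglycemia by arm; SAP 4.4.4 contradicts this. What is missing is a by-arm summary of the measured values.

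A reader might also infer that the 6, 12 and 24 hour glucose values are wasted. They are not. The Laboratory form asks whether each value is normal and, if not, clinically significant, and sends significant post-device values to the Adverse Event form. They have an indirect use but no direct summary.

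A third tempting inference is that site practice on insulin drives the event count. The definition also admits values that would be repeated, and randomization is stratified by site in blocks of two or four. Site practice may move the overall rate but should be balanced between arms.

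Nor do the rabbit data show that only the first draw matters. Section 3.2.18 says "By 4 hours, glucose levels for all three groups were similar and remained normal for the remainder of the study". In that same study, however, the sham group also rose at 1 hour, PerClot and Arista were almost equal at 2 hours, and surgical stress was given as the likely cause. Section 3.2.17, at a larger dose, reports the groups as similar only by 48 hours, a time absent from its own sampling list. Neither study establishes a difference between PerClot and Arista.

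For C3, the objector can say that R95 is low probability and that immune consequences such as anaphylaxis and fever are event lines. That is fair, but those are downstream events, not C3 change. Finally, SAP 4.4.4 calls its safety analyses descriptive, so low Fisher power breaks no stated aim. That also stands, and it favors descriptive tables over further tests.

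**Conclusion.** The point holds as a gap in the safety analysis of measured values, worth correcting but not critical. For glucose, the existing event analysis depends on an unblinded judgement of clinical significance and, outside the two restricted classes, on 17 of 324 subjects having the event. At assumed true rates of 2% and 8%, the threshold lowers the chance of a comparison that is both made and significant from 0.63 to 0.35. At 5% and 15% it changes nothing. For C3 the gap is wider, because no event line exists.

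These sizes rest on assumed event rates, assumed glucose SDs, a two-sided 0.05 level and complete data. That the draws were scheduled because of the named risks is an inference; Protocol 6.4.4 does not state the purpose.

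The window discrepancy is real but small: one of four post-device glucose draws, in a footnote on a sample draft form, with draw time recorded. It would be wrong to infer from it that a device difference will be hidden.

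**What to change.** Add two descriptive by-arm tables to SAP 4.4.4, on the ITT population already specified for safety:

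- Glucose change from the post-randomization, pre-device value at each scheduled time, with mean difference and 95% confidence interval, and use of glucose-lowering medication shown alongside.
- C3 change from the preoperative value, with mean difference and 95% confidence interval.

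Label both as descriptive. State that, because the control is also a starch hemostat, they show relative rather than absolute effect.

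Separately, reconcile the first post-device glucose window between Protocol 6.4.4 and the Laboratory form footnote, and use the recorded draw time in the analysis.

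The cost is a short SAP amendment, some programming and one wording correction. Draw time and medication use are already captured, so no new draws and no change in sample size are needed. The small downside is more unadjusted comparisons.

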4.5 Subgroup Analysis

Analyses will be conducted to determine the consistency of study results across the following subgroups: gender, race, and bleeding severity score. These analyses will be descriptive in nature, and as such there are no formal hypothesis tests. There are no labeling claims being sought out for these subgroups analyses.

Subgroup analyses will be performed on the primary efficacy measure (proportion achieving hemostasis at 7 minutes), secondary efficacy measure (proportion achieving hemostasis at 5 minutes), and safety measures (proportion with device related events and serious adverse events). For efficacy measures, analyses will be performed on the AT population. Safety subgroup analyses will be based on the ITT population.

For each endpoint measure the proportion of subjects will be reported by subgroup. The difference in proportions and its associated 95% confidence interval will be reported by subgroup. To test for a differential treatment effect across subgroups a logistic regression model will be fit, testing for the interaction of treatment group by subgroup. In the case that poolability across a subgroup is questionable, as indicated by statistical significance of the interaction effect at $\alpha \leq 0.05$, the estimated treatment difference and 95% confidence interval from the subgroup adjusted logistic regression model will be reported.

4.6 Covariate Analysis

Covariate analyses will be performed to assess the association with certain study parameters on the primary efficacy endpoint. These models will be fit using logistic regression, measuring the odds of primary efficacy success. All models will include treatment group as a covariate. Covariates found to be significant at a 0.1 alpha level in the univariate assessment will be included in a multivariable model. After the multivariable model is fit, covariates will remain in the final multivariable model if they maintain significance at a 0.1 alpha level. For both univariate and multivariate models, the model derived estimates (i.e. beta estimates) for the association with primary efficacy success will be displayed, along with the Type III p-values. An adjusted estimate of the difference between proportions and associated 95% confidence interval (treatment versus control) will be obtained from the multivariable model.

Covariate assessments may consist of, but are not limited to, the following variables:

- Demographic measures such as age, gender, ethnicity, and BMI;
- Medical history;
- Therapeutic area;

- Use of blood modifiers or products known to affect bleeding (including aspirin and colloids);;
- Administration of blood products;
- Fluids administered (including colloids and crystalloids);
- Surface area of the anatomic site;
- Initial bleeding severity (as continuous measure);
- Indication for surgery;
- Complete blood count and coagulation status;
- Complement C3;
- Smoking history;
- Use of oral contraceptives;
- Diabetes;
- Presence of any malignancies;
- Amount of hemostat applied;
- Core body temperature;
- Level of glycosylated hemoglobin;
- Other hemostatic efforts made;
- Procedure type;
- NNIS risk index;
- Blood glucose at randomization;
- Blood glucose within 1 hour of device application;
- American Society of Anesthesiologists Classification;
- Total operative time;
- Placement of wound drain;
- Drainage volume within 24 hours postoperatively;
- Total drainage volume;
- Total drainage duration; and
- Volume of fluid used to rinse away excess study device.

In the event that a covariate is significant at the 0.05 alpha level in the univariate assessment, an additional model will be fit to test for an interaction effect of treatment and that covariate.

